3.4.2. Baseline characteristics

Randomization is stratified by the following, as recorded in the Interactive Response Technology (IRT) system:

- ECOG PS (0 vs 1);
- Region (United States vs Canada/Western Europe vs the rest of the world).

The primary analyses of PFS and OS for PD-L1 positive patients, as well as the secondary analyses of PFS and OS for patients unselected for PD-L1 expression will be stratified by these randomization stratification factors.

Other baseline characteristics (including demographics, physical measurements, disease history and prior anti-cancer therapies) are described in Section 6.5.1. These baseline characteristics are not planned to be included as stratification variables or covariates in statistical models unless otherwise specified in Section 6.

3.5. Safety Endpoints

3.5.1. Adverse events

Treatment-Emergent Adverse Events

Treatment-emergent adverse events (TEAEs) are those events with onset dates occurring during the on-treatment period for the first time, or if the worsening of an event is during the on-treatment period.

On-treatment period is defined as the time from the first dose of study treatment through minimum (30 days + last dose of study treatment, start day of new anti-cancer drug therapy – 1 day). The start day of new anti-cancer drug therapy after the first dose of study treatment is derived as outlined in Section 5.2.5.

Adverse Events of Special Interest (AESIs)

AESIs are immune-related adverse events (irAE) and infusion-related reactions (IRRs). The criteria for classification of an AE as an irAE or IRR are described in Appendices 1 and 2, respectively.

3-Tier Adverse Events

It should be recognized that most studies are not designed to reliably demonstrate a causal relationship between the use of a pharmaceutical product and an adverse event or a group of adverse events. Except for select events in unique situations, studies do not employ formal adjudication procedures for the purpose of event classification. As such, safety analyses are generally considered as an exploratory analysis and its purpose is to generate hypotheses for further investigation. The 3-tier approach facilitates these exploratory analyses.

Adverse events and clusters of adverse events, of any causality and treatment-related, will also be summarized following a 3-tier approach. Under this approach, AEs are classified into 1 of 3 tiers.

Tier-1 events: These are pre-specified events or clusters of events of clinical importance and will be described in the Safety Review Plan.

Tier-2 events: These are events that are not Tier-1 but are “common”. A MedDRA PT is defined as a Tier-2 event if it is reported by

- a) at least 10% of patients with any grade in any treatment arm, or
- b) at least 5% of patients with Grade 3, 4 or 5 in any treatment arm.

Tier-3 events: All other AEs that are classified neither as Tier-1 nor Tier-2.

4. ANALYSIS SETS

Data for all patients will be assessed to determine if patients meet the criteria for inclusion in each analysis population prior to releasing the database and classifications will be documented per Pfizer’s standard operating procedures.

Only patients who signed informed consent will be included in the analysis sets below.

Table 4 summarizes the use of the analysis sets for efficacy, safety, baseline characteristics and exposure.

Table 4. Statistical Analyses by Analysis Set

Endpoints	Full Analysis Set	Per Protocol Analysis Set	Safety Analysis Set
Baseline Characteristics	✓		✓
Prior and Concomitant Therapies	✓		✓
Exposure			✓
Efficacy: Primary	✓	✓	
Efficacy: Secondary	✓	✓ (key secondary only*)	
CCI			
Safety			✓

* key secondary endpoints are OS and PFS for patients unselected for PD-L1 expression

4.1. Full Analysis Set

The full analysis set (FAS) will include all randomized patients. Patients will be classified according to the study treatment assigned at randomization.

4.2. Safety Analysis Set

The safety analysis set will include all patients who receive at least one dose of study drug. Patients will be classified according to the study treatment assigned at randomization unless the incorrect treatment(s) was/were received throughout the dosing period in which case patients will be classified according to the first study treatment received.

4.3. Other Analysis Sets

4.3.1. Per-protocol analysis set

Per protocol (PP) analysis set is a subset of the FAS and will include patients who do not meet any of the following criteria that could impact the key objectives of the study. Patients who meet any of the following criteria will be excluded from the PP analysis set.

- Patient did not receive at least one dose of the randomized study treatment;
- *Applicable only for PFS:* Patient without a tumor assessment ≥ 6 weeks after randomization (unless PD by BICR or death is observed before that time in which case the patient will not be excluded from the PP analysis set);
- *Applicable only for PFS:* Patient without measurable disease at baseline by BICR;
- ECOG status > 1 ;
- Any prior therapies as defined by the exclusion criterion 1 of the study protocol:
 - Prior systemic therapy directed at advanced or metastatic RCC.
 - Prior adjuvant or neoadjuvant therapy for RCC if disease progression or relapse has occurred during or within 12 months after the last dose of treatment.

- Prior immunotherapy with IL-2, IFN- α , or anti-PD-1, anti-PD-L1, anti-PD-L2, anti-CD137, or anti-cytotoxic T-lymphocyte-associated antigen-4 (CTLA-4) antibody (including ipilimumab), or any other antibody or drug specifically targeting T-cell co-stimulation or immune checkpoint pathways.
- Prior therapy with axitinib and/or sunitinib as well as any prior therapies with other VEGF pathway inhibitors.

Note that the protocol only requires that patients have measurable disease at baseline as per investigator assessment. However, since PFS by BICR is a primary endpoint, “patients without measurable disease at baseline by BICR” will be used as a criterion to exclude patients from the PP analysis set for the sensitivity analysis of the PFS by BICR endpoint.

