6.1.1.1. Primary analysis

The following analyses will be based on the FAS using the strata assigned at randomization. PD below refers to PD by BICR assessment.

Progression-Free Survival (PFS) is defined as the time from the date of randomization to the date of the first documentation of PD or death due to any cause, whichever occurs first.

PFS data will be censored on the date of the last adequate tumor assessment for patients who do not have an event (PD or death), for patients who start a new anti-cancer therapy prior to an event (see Section 5.2.6) or for patients with an event after 2 or more missing tumor assessments. Patients who do not have an adequate baseline tumor assessment or who do not have an adequate post-baseline tumor assessment will be censored on the date of randomization unless death occurred on or before the time of the second planned tumor assessment (i.e., ≤ 12 weeks after the date of randomization) in which case the death will be considered an event.

In this study antitumor activity will be assessed through radiological tumor assessments conducted at screening and every 6 weeks (+7 days window allowed) until PD regardless of initiation of subsequent anti-cancer therapy. After 18 months from the date of randomization, tumor assessments will be conducted less frequently, i.e., at 12-week intervals (+7 days window allowed).

The censoring and event date options to be considered for the PFS and DR analysis are presented in Table 9.

$$\text{PFS (months)} = [\text{date of event or censoring} - \text{date of randomization} + 1] / 30.4375$$

Table 9. Outcome and event dates for PFS and DR analyses

Scenario	Date of event/censoring	Outcome
No adequate baseline assessment	Date of randomization	Censored ^a
PD or death 
 - After at most one missing or inadequate post-baseline tumor assessment, OR - ≤ 12 weeks after the date of randomization 	Date of PD or death	Event
PD or death after 2 or more missing or inadequate post-baseline tumor assessments	Date of last adequate tumor assessment ^b documenting no PD before new anti-cancer therapy is given or missed tumor assessments	Censored
No PD and no death	Date of last adequate tumor assessment ^b documenting no PD before new anti-cancer therapy is given or missed tumor assessments	Censored

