Treatment discontinuation due to 'Disease progression' without documented progression	Not applicable	Information is ignored. Outcome is derived based on documented progression only.
New anti-cancer therapy given	Date of last adequate tumor assessment ^b documenting no PD before new anti-cancer therapy is given or missed tumor assessments	Censored

^a However if the patient dies ≤12 weeks after the date of randomization the death is an event with date on death date

^b If there are no adequate post-baseline assessments prior to PD or death, then the time without adequate assessment should be measured from the date of randomization; if the criteria were met the censoring will be on the date of randomization.

The primary efficacy analysis will compare the PFS time based on BICR assessment between the experimental arm and the control arm, and will be performed using a 1-sided stratified log-rank test as described in Section 5.1.

The treatment effect will be estimated using a Cox's Proportional Hazard model stratified by the randomization strata to calculate the hazard ratio. Each stratum will define a separate baseline hazard function (using the 'STRATA' statement in SAS PROC PHREG), i.e. for the i-th stratum the hazard function is expressed as: $h(i;t) = h(i,0;t) \exp(x\beta)$, where $h(i,0;t)$ defines the baseline hazard function for the i-th stratum and x defines the treatment arm (0=control arm, 1= experimental arm) and β is the unknown regression parameter.

Ties will be handled by replacing the proportional hazards model by the discrete logistic model (Ties=Discrete option in SAS PROC PHREG).

In order to account for the group sequential design in this study, the repeated CI (RCI) method (Jennison and Turnbull, 2000) will be used to construct the 2-sided RCIs for the hazard ratio at the interim and the final analyses of PFS. In addition, the unadjusted 95% CIs for the hazard ratio will also be reported at the interim and the final analyses for PFS.

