6.2.2.3. Sensitivity analyses for progression-free survival

All sensitivity analyses will be performed for PD-L1 positive patients and for patients unselected for PD-L1 expression.

The following sensitivity analyses will be performed to explore the robustness of the primary analysis results. These analyses are regarded as purely exploratory. The sensitivity analyses will repeat the primary analysis (p-value, HR and 95% CIs) described in Section 6.1.1.1 with the modifications below:

- PFS based on BICR assessment and counting all PD and deaths as events regardless of missing assessments or timing of the event
- PFS based on BICR assessment on the PP analysis set for PFS
- PFS based on BICR assessment using an unstratified analysis
- PFS based on BICR assessment using strata derived according to eCRF data instead of those entered in IRT
- PFS based on BICR assessment modifying the censoring rules in Table 9 to consider all deaths as events
- PFS based on BICR assessment modifying the censoring rules in Table 9 with initiation of subsequent anti-cancer therapies not used as a censoring reason.

Methods for evaluating the validity of model assumptions

The proportional hazards assumption will be checked visually by plotting $\log(-\log(\text{PFS}))$ versus $\log(\text{time})$ within each randomization stratum.

Schoenfeld residuals for the stratified Cox proportional regression model will be plotted to investigate graphically violations from the proportional hazards (PH) assumption; a non-zero

slope is evidence of departure from PH. The PH assumption will be formally tested using Schoenfeld's residual test (Schoenfeld, 1980; Therneau & Grambsch, 2000). Large departures from PH will be evidenced by a p-value <0.05.

If these show large departures from proportional hazards, then PFS by BICR assessment will also be analyzed based on restricted mean survival time (RMST) differences (Zhang, 2013).

Restricted Mean Survival Time (RMST)

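### The per-protocol set for PFS removes some week 6 to 12 deaths that the primary analysis counts as events

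*SAP*

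**What the plan says.** SAP 4.3.1 defines the PP set as a subset of the full analysis set (FAS). One criterion that applies to PFS alone removes any patient who has no tumor assessment at 6 weeks or later, "unless PD by BICR or death is observed before that time in which case the patient will not be excluded".

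SAP 6.1.1.1 sets the primary PFS rule. A patient with no adequate baseline or no adequate post-baseline assessment is censored at the randomization date "unless death occurred on or before the time of the second planned tumor assessment (i.e., ≤ 12 weeks after the date of randomization"; such a death counts as an event. Table 9 agrees: PD or death at 12 weeks or earlier is an event. Scans are due "every 6 weeks (+7 days window allowed) until PD regardless of initiation of subsequent anti-cancer therapy", so an on-schedule first scan can fall anywhere from week 6 to week 7.

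The PP set is used in SAP 6.2.2.3, which lists "PFS based on BICR assessment on the PP analysis set for PFS" among the sensitivity analyses, for PD-L1 positive and unselected patients. Protocol 9.2.2 describes the PP set as treated patients without major protocol deviations that could affect the primary objective, leaves the list of deviations to the SAP, and names the set as a sensitivity analysis for the primary efficacy endpoints.

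**The concern.** The two cut-offs do not match. The exception in the PP definition stops at week 6; the primary rule protects deaths until week 12. Between the two, a death with no scan at 6 weeks or later is an event in one analysis and the patient is absent from the other.

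A per-protocol set should exclude patients for deviations. Dying before a scan is not a deviation, and a patient who dies in week 6 to 7, still inside the scan window, has not missed a scan at all. The existing exception suggests the authors meant to keep patients whose event explains the missing scan; the cut-off was simply not aligned with Table 9.

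What is at stake is how one sensitivity analysis can be interpreted. If PP and FAS results for PFS differ, part of the difference could come from removed deaths rather than from protocol adherence.

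**Working it through.** **1. The plan's event target.** It serves here only as a denominator. Inputs from SAP 5.1.1: HR 0.65, one-sided alpha 0.004, power 90%. Schoenfeld: d = 4(z₀.₉₉₆ + z₀.₉₀)² / (ln 0.65)² = 4(2.652 + 1.282)² / 0.1856 ≈ 334, against 336 stated. With 336 events and the two PFS efficacy boundaries in SAP Table 5 (−3.2493, −2.6682), the design gives alpha 0.0040 and power 90.1%. The target reproduces and is not in dispute.

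**2. Both rules applied to the same patients** (no PD and no new anti-cancer therapy before death; any scan listed is adequate).

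| Death | Scans | Primary PFS | PP set for PFS |
|---|---|---|---|
| Week 4 or 5.9 | none | event | kept |
| Week 6.5, 8 or 12 | none | event | **excluded** |
| Week 8 | week 5.5 only | event | **excluded** |
| Week 8 | week 6.2 | event | kept |
| Week 13 | none | censored at randomization | excluded |
| Week 13 | week 5.5 only | event (at most one assessment missing) | **excluded** |

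**3. Which primary events the criterion can remove.** PD at 6 weeks or later needs a scan at 6 weeks or later, so it always meets the criterion. PD or death before week 6 is exempt. That leaves deaths in weeks 6 to 12 with no scan at 6 weeks or later, plus the rare early-scan case in the last row. Living patients with no adequate post-baseline scan are also excluded, but the primary analysis already censors them at randomization, so removing them changes almost nothing.

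**4. Size of the affected group.** Inputs from SAP 5.1.1: 580 PD-L1 positive and 830 total patients, randomized 1:1; median OS 26.4 months (Arm B), and 37.7 (PD-L1 positive) or 35.2 (unselected) months in Arm A; exponential survival. With λ = ln 2 / median and t = weeks × 7 / 30.4375 (week 6 = 1.380, week 7 = 1.610, week 12 = 2.760 months), P(death between t₁ and t₂) = exp(−λt₁) − exp(−λt₂).

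| Population, arm | n | P, wk 6–12 | Deaths | P, wk 6–7 | Deaths |
|---|---|---|---|---|---|
| PD-L1 positive, A | 290 | 0.0244 | 7.1 | 0.0041 | 1.2 |
| PD-L1 positive, B | 290 | 0.0343 | 10.0 | 0.0058 | 1.7 |
| Unselected, A | 415 | 0.0261 | 10.8 | 0.0044 | 1.8 |
| Unselected, B | 415 | 0.0343 | 14.2 | 0.0058 | 2.4 |

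Totals, summed before rounding:
- PD-L1 positive: 17.0 deaths in weeks 6–12 (17.0/336 = 5.1% of events), of which 2.9 (0.9%) in weeks 6–7.
- Unselected: 25.1 deaths (25.1/490 = 5.1%), of which 4.2 (0.9%) in weeks 6–7.

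The week 6–12 totals are ceilings, because they assume that nobody in the group had a scan at 6 weeks or later. The documents do not give that share. If it is 10%, 25%, 50% or 100%, about 2, 4, 9 or 17 PD-L1 positive events are dropped (about 3, 6, 13 or 25 unselected).

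**The case against.** The strongest reply is that little depends on this analysis. SAP 6.2.2.3 says of the sensitivity analyses, "These analyses are regarded as purely exploratory". The same section plans two further PFS analyses, not restricted to the PP set, that relax the censoring rules so that all deaths count. The criterion applies to PFS alone, so the PP analysis of OS keeps these patients. SAP 6.6.2 tabulates deaths and their causes. All of this stands and limits the consequence. It does not repair the PP set: the two other analyses change the censoring rules and leave PP membership as it is.

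The ceiling is also generous. An on-schedule patient who dies after week 7 has already been scanned and stays in. Protocol 4.1 requires an estimated life expectancy of at least 3 months, so a constant hazard probably overstates early deaths. Both points stand.

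The phrase about time could be read as the time of the missing assessment, which would keep these deaths. That is possible, but 6 weeks is the only time named, and two programmers could build different sets. The ambiguity supports clarifying the text.

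Three stronger readings are tempting, and the documents do not support them:
- **The rule hides early fatal toxicity.** The deaths remain in the FAS, in OS and in the safety tables.
- **The rule favours the combination.** That needs an excess of unscanned deaths in Arm A in this window, and no such rate is given. In the Phase 1b study, 1 of 47 treated patients died of myocarditis before the first tumor assessment (Protocol 1.2.3), but the week is not stated; a death before week 6 would be kept.
- **Agreement between PP and FAS would be an artefact.** Dropping events can only make the two differ. If they agree, the dropped deaths did not matter.

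**Conclusion.** The mismatch is real on the wording as it stands. SAP 4.3.1 can remove patients whose death is a PFS event under SAP 6.1.1.1, with no protocol deviation on their part, and early-scan cases aside these deaths are the only primary events the criterion can remove. It is worded on scans but selects on outcome in effect.

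The size is probably small: at most about 17 of 336 PD-L1 positive events or 25 of 490 unselected, with about 3 and 4 deaths respectively inside the allowed first-scan window. These figures rest on exponential OS at the planning medians; the ceiling further assumes that no affected patient had a qualifying scan. If the dropped deaths split between arms as those medians imply (7.1 to 10.0, a ratio of 0.71, close to the planned PFS hazard ratio of 0.65), little shift in the PP hazard ratio is expected. The actual split is not given, so neither the size nor the direction of any bias can be stated. The primary test, alpha and event targets are untouched. Severity: minor.

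**What to change.** In the PFS-only scan criterion of SAP 4.3.1, replace the exception with: *unless the patient has a PFS event under the primary rules in Table 9*. No event of the primary analysis is then removed by this criterion, in either population.

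Moving the cut-off from 6 to 12 weeks would be simpler but incomplete. A patient with an adequate non-PD scan at week 5.5 who dies at week 13 is an event under Table 9 and would still be excluded.

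The cost is one line of SAP wording. The PP set becomes slightly larger and its PFS result may be slightly less favourable.

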4.3.2. PK analysis sets

The PK concentration analysis set is a subset of the safety analysis set and will include patients who have at least one post-dose concentration measurement above the lower limit of quantitation (LLQ) for avelumab or axitinib.

The PK parameter analysis set is a subset of the safety analysis set and will include patients who have at least one of the PK parameters of interest for avelumab or axitinib.

4.3.3. Biomarker analysis set

The biomarker analysis set for biomarkers that are measured only at screening is a subset of the safety analysis set and will include patients who have at least one screening biomarker assessment.

The biomarker analysis set for biomarkers that are measured sequentially is a subset of the safety analysis set and will include patients who have at least one baseline and one on-treatment biomarker assessment for the same marker.

Analysis sets will be defined separately for blood-based and tumor tissue-based biomarkers.

4.3.4. Immunogenicity analysis set

The immunogenicity analysis set is a subset of the safety analysis set and will include patients who have at least one ADA/nAb sample collected for avelumab in Arm A.

4.3.5. PRO analysis set

The PRO analysis set will include all randomized patients (FAS).

5. GENERAL METHODOLOGY AND CONVENTIONS

5.1. Hypotheses and Decision Rules

All references to PFS in Section 5.1.1 and Section 5.1.2 refer to PFS by BICR assessment even when not specifically stated.

5.1.1. Hypotheses and sample size determination

The following statistical hypotheses will be tested to address the primary objectives:

$$H_{01}: HR_{PFS+} \geq 1 \text{ vs } H_{11}: HR_{PFS+} < 1$$

$$H_{02}: HR_{OS+} \geq 1 \text{ vs } H_{12}: HR_{OS+} < 1$$

where HR_{PFS+} and HR_{OS+} are the hazard ratios (Arm A vs. Arm B) of PFS and OS, respectively, in PD-L1 positive patients.

In addition the following statistical hypotheses will be tested to address the secondary objectives:

[figure not shown]
$$H_{03}: HR_{PFS} \geq 1 \text{ vs } H_{13}: HR_{PFS} < 1$$

$$H_{04}: HR_{OS} \geq 1 \text{ vs } H_{14}: HR_{OS} < 1$$

where HR_{PFS} and HR_{OS} are the hazard ratios (Arm A vs. Arm B) of PFS and OS, respectively, for patients unselected for PD-L1 expression.

Overall type I-error will be maintained at or below 1-sided 0.025 by allocating $\alpha=0.004$ (α_1) to the PFS comparison in PD-L1+ patients and by allocating $\alpha=0.021$ (α_2) to the OS comparison in PD-L1 positive patients. A gatekeeping procedure will be used to allow further testing of PFS and OS for patients unselected for PD-L1 expression as described in Figure 1. The significance levels for each test will also take into account the group sequential nature of the design.

Figure 1 Testing Strategy

Approximately 830 patients, including a minimum of 580 PD-L1 positive patients, will be randomized to the treatment arms using a 1:1 randomization, stratified by ECOG PS (0 vs 1) and region (United States vs Canada/Western Europe vs the rest of the world).

For the primary PFS comparison, 336 PFS events by BICR assessment for PD-L1 positive patients will be required to have at least 90% power to detect a hazard ratio of 0.65 using a 1-sided log-rank test at a significance level of 0.004, and a 2-look group sequential design with Lan-DeMets (O'Brien-Fleming) α -spending function to determine the efficacy boundary and a Gamma Family (-15) β -spending function to determine the non-binding futility boundary.

For the primary OS comparison, 368 OS events for PD-L1 positive patients will be required to have at least 90% power to detect a hazard ratio of 0.70 using a 1-sided log-rank test at a significance level of 0.021, and a 4-look group-sequential design with Lan-DeMets (O'Brien-Fleming) α -spending function to determine the efficacy boundary and a Gamma Family (-3) β -spending function to determine the non-binding futility boundary.

The sample size for this study is determined based on the following:

1. the median PFS for patients receiving sunitinib is 11 months (Sutent Summary of Product Characteristics) and the median PFS for patients receiving avelumab in combination with axitinib is 16.9 months for PD-L1 positive patients and 15.7 months for patients unselected for PD-L1 expression; this, corresponds to a hazard ratio (HR) of 0.65 and 0.7, respectively under the exponential model assumption;
2. the median OS for patients receiving sunitinib is 26.4 months (Sutent Summary of Product Characteristics) and the median OS for patients receiving avelumab in combination with axitinib is 37.7 months for PDL1 positive patients and 35.2 months for patients unselected for PD-L1 expression; this corresponds to a HR of 0.7 and 0.75, respectively under the exponential model assumption;

3. PFS drop-out rate of approximately 15% and OS drop-out rate of approximately 5%;
4. 70% of the randomized patients are PD-L1 positive;
5. non-uniform patient accrual accomplished over a 21 month period.

The sample size of approximately 830 patients will also allow an assessment of PFS and OS in patients unselected for PD-L1 expression.

If H_{01} is rejected then PFS in patients unselected for PD-L1 expression can be tested and 490 PFS events by BICR assessment will be required to have at least 90% power to detect a HR of 0.70 using a 1-sided log rank test at a significance level of 0.004, and a 2-look group sequential design with Lan-DeMets (O'Brien-Fleming) α -spending function to determine the efficacy boundary.

If either H_{02} or H_{03} are rejected, then OS in patients unselected for PD-L1 expression can be tested at the sum of the significance levels associated with the significant H_{02} and H_{03} tests (see Figure 1). With 534 OS events, the power is 91% (if both H_{02} and H_{03} are rejected), 90% (if H_{02} is rejected and H_{03} is not rejected) or 74% (if H_{02} is not rejected and H_{03} is rejected) to detect a HR of 0.75 using a 1-sided log rank test at a significance level of 0.025, 0.021 or 0.004, respectively, and a 4-look group sequential design with Lan-DeMets (O'Brien-Fleming) α -spending function to determine the efficacy boundary.

The data cutoff for the primary PFS analysis will occur after the target number of PFS events by BICR assessment in PD-L1 positive patients has been reached and the last patient randomized in the study has been followed for at least 12 months after randomization.

The data cutoff for the primary OS analysis will occur after the target number of deaths in PD-L1 positive patients has been reached.

The study will be considered positive if the stratified log-rank test for either PFS or OS in PD-L1 positive patients is significant at the respective α levels.

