If  $H_{01}$  is rejected then PFS in the 'all comers' population can be tested and 490 PFS event by BICR assessment will provide 90% power to detect a HR of 0.70 using a 1-sided log rank test at a significance level of 0.004, and a 2-look group sequential design with Lan-DeMets (O'Brien-Fleming)  $\alpha$ -spending function to determine the efficacy boundary.

If either  $H_{02}$  or  $H_{03}$  are rejected, then OS in the 'all comers' population can be tested at the sum of the significance levels associated with the significant  $H_{02}$  and  $H_{03}$  tests (see Figure 2). With 534 OS events, the power is 91% (if both  $H_{02}$  and  $H_{03}$  are rejected), 90% (if  $H_{02}$  is rejected and  $H_{03}$  is not rejected) or 74% (if  $H_{02}$  is not rejected and  $H_{03}$  is rejected) to detect a HR of 0.75 using a 1-sided log rank test at a significance level of 0.025, 0.021 or 0.004, respectively, and a 4-look group sequential design with Lan-DeMets (O'Brien-Fleming)  $\alpha$ -spending function to determine the efficacy boundary.

The data cutoff for the primary PFS analysis will occur after the target number of PFS events by BICR assessment in the PD-L1+ population has been reached and the last patient randomized in the study has been followed for at least 12 months after randomization.

The data cutoff for the primary OS analysis will occur after the target number of deaths in the PD-L1+ population has been reached.

The study will be considered positive if the stratified log-rank test for either PFS or OS in the PD-L1+ population is significant at the respective  $\alpha$  levels.

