Number of events ^a (Information fraction)	343 (70%)	490 (100%)	182 (34%)	283 (53%)	427 (80%)	534 (100%)

Endpoint	PFS in patients unselected for PD-L1 expression		OS in patients unselected for PD-L1 expression			
	IA1	PA	IA1	IA2	IA3	PA
Analysis cutoff trigger	235 PFS events in PD-L1+	336 PFS events in PD-L1+	235 PFS events in PD-L1+	336 PFS events in PD-L1+	15 months after IA2	368 deaths in PD-L1+
fraction)						
p-value (z-value) for efficacy ^b	<0.0006 (<-3.2478)	<0.0038 (<-2.6683)	<0.00012 (<-3.6656)	<0.0020 (<-2.8726)	<0.0115 (<-2.2727)	<0.0212 (<-2.0286)
^a Number of events expected under H ₁₃ for PFS (assuming a HR of 0.7) and H ₁₄ for OS (assuming a HR of 0.75). ^b The p-values and z-values noted for OS are those associated with the scenario when both H ₀₂ and H ₀₃ are rejected. IA1 = interim analysis 1, IA2 = interim analysis 2, IA3 = interim analysis 3, PA = primary analysis The observed number of events at the IAs may not match the planned number of events. The efficacy and futility boundaries will be updated based on the actual number of observed events using the pre-specified α -spending functions.						

Since the observed number of events at the interim analysis may not be exactly equal to the planned number of events, the efficacy and futility boundaries will be updated based on the actual number of observed events using the pre-specified α - and β -spending functions. Therefore, the observed Z-test statistic at the interim analysis will be compared with the updated efficacy and, for the primary endpoints, futility boundaries. If the study continues to final analysis, the p-value that will be used to declare statistical significance at the final analysis for each endpoint will be based on the actual number of events documented at the cut-off date for the final analysis, the α already spent at the interim analysis and the gatekeeping testing strategy. Further details are provided in Section 7.

Based on the stopping boundaries defined above and the timing of the interim and final analyses as described above, the design has the following operating characteristics.

Table 7 Simulated cumulative probabilities to stop for efficacy or futility at the interim or final PFS analysis in PD-L1 positive patients

Scenario	Look	Number of PFS events	Calendar Time (months)	P(Reject H ₀₁)	P(Reject H ₁₁)
H ₀₁ is true (HR=1)	Interim	235	23	0.0008	0.5933
	Final	336	29	0.0049	0.9951
H ₁₁ is true (HR=0.65)	Interim	235	25	0.5088	0.0011

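### Is the 74% power for overall survival in all comers wrong because it is tied to a failed test in PD-L1-positive patients?

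*SAP*

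**What the plan says.** Under SAP 5.1.1, H04 may be tested once H02 or H03 is significant. Its level is the sum of the levels of whichever of the two succeeded: 0.021 comes from H02 and 0.004 from H03.

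The next sentence gives the power with 534 deaths: 91% if both succeed, 90% if only H02 does, and "74% (if H_{02} is not rejected and H_{03} is rejected) to detect a HR of 0.75". It continues "using a 1-sided log rank test at a significance level of 0.025, 0.021 or 0.004, respectively", "and a 4-look group sequential design with Lan-DeMets" O'Brien-Fleming spending. Protocol 9.1 (text after Figure 2) and the Protocol Summary carry the same sentence.

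SAP 5.1.2, Table 6, prints the H04 boundaries for one of these scenarios only. Footnote b explains: "The p-values and z-values noted for OS are those associated with the scenario when both" H02 and H03 are rejected.

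**The concern.** A probability followed by an if-clause that names trial results looks like a conditional probability. H02 and H04 are far from independent: 368 of the 534 planned deaths are in PD-L1-positive patients. If H02 fails, H04 will probably look weak too, and 74% seems much too optimistic for that case.

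H04 is one of the two key secondary hypotheses named under SAP Table 4. If the figure really were offered as the chance of an all-comers survival claim after the PD-L1-positive claim had failed, it would mislead anyone judging the value of that route.

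**Working it through.** **Inputs.** From SAP 5.1.1: 534 deaths, 1:1 randomization, HR 0.75 in all comers and 0.70 in PD-L1-positive patients, one-sided levels 0.025, 0.021 and 0.004. From SAP Tables 5 and 6: deaths by look of 182/283/427/534 (all comers) and 125/195/294/368 (PD-L1-positive).

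**1. The printed powers as ordinary powers, single look.** Power = Φ(√(D/4)·|ln HR| − z). Here √(534/4) × |ln 0.75| = 11.554 × 0.2877 = 3.324.

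| Level | z | 3.324 − z | Single look | Four looks | Printed |
|---|---|---|---|---|---|
| 0.025 | 1.960 | 1.364 | 91.4% | 90.8% | 91% |
| 0.021 | 2.034 | 1.290 | 90.2% | 89.6% | 90% |
| 0.004 | 2.652 | 0.672 | 74.9% | 74.3% | 74% |

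**2. Four looks.** The table's four-look column uses Lan-DeMets O'Brien-Fleming boundaries at the Table 6 death counts. At 0.025 they come out at 3.6656/2.8726/2.2727/2.0286, the same as Table 6 apart from sign. At 0.004 they are 4.7929/3.7856/3.0205/2.6878. All three four-look powers round to the printed figures.

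**3. The conditional reading.** The final statistics for H02 and H04 correlate at √(368/534) = 0.83. HRs of 0.70 and 0.75 imply a value for the remaining patients that the plan does not state: exp[(534 ln 0.75 − 368 ln 0.70)/166] = 0.874. A joint simulation of both tests over four looks, with non-binding futility ignored, gives:

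- P(H02 rejected) = 91.2%
- P(H04 rejected at 0.004, given H02 rejected) = 80.6%
- P(H04 rejected at 0.004, given H02 not rejected) = 9.0%

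These average back to 0.912 × 0.806 + 0.088 × 0.090 = 0.735 + 0.008 = 0.743. So the printed 74% is the power at level 0.004 averaged over both H02 results.

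**4. Which quantity the sentence states.** It names one hazard ratio, one death count, one test and three levels, which is all that an ordinary power needs. A power conditional on H02 and H03 would also need the PD-L1-positive hazard ratio and a PFS-OS correlation. The sentence gives neither, and the correlation is in neither document.

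The paragraph before it has the same form: if H01 is rejected, 490 events give 90% power for PFS in all comers at 0.004. That too is an ordinary power: √(490/4) × |ln 0.70| = 11.068 × 0.3567 = 3.948, less 2.652 is 1.296, and Φ = 90.2% for a single look. The if-clause there says when the test is allowed.

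**The case for a change.** The best case for the concern is that no sentence says these powers are unconditional. Footnote b of Table 6 is only a partial parallel: it labels boundaries, which depend on the level alone, while a chance of success does change with the result of a correlated test. A reader who asks how likely an all-comers survival claim is after H02 fails could take 74% as the answer.

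Two things stand. Under the planning hazard ratios that chance is about 9%, and the plan does not print it. But the plan does not set out to give it, and the figure is not stable enough to serve as a correction:

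- With the all-comers HR held at 0.75, it rises to 28%, 49%, 63% and 70% as the PD-L1-positive HR goes to 0.75, 0.80, 0.85 and 0.90.
- Requiring H03 to be rejected as well gives about 9% to 14% for an assumed PFS-OS correlation of 0 to 0.7, depending on how the correlation is modelled.
- For the 90% label, the same full conditioning gives anything from about 71% to 95%, so even the direction of the supposed error is unsettled.
- The 9% assumes that H02 fails at every look. SAP 7.1 lets H04 be tested at the first or second interim once H03 succeeds, when H02 may only be not yet rejected. SAP Table 8 puts cumulative rejection of H02 at 0.3095 by the second interim, under HR 0.70.

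**Conclusion.** The concern does not hold. The H02 and H03 results in the sentence select the level for H04. At each selected level the printed power agrees with the recomputed one after rounding: 90.8%, 89.6% and 74.3% against 91%, 90% and 74%. This rests on the plan's own inputs: 1:1 allocation, a constant HR of 0.75, 534 deaths, looks at the Table 6 counts, and no futility rule for H04 (SAP 7.2.4).

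The 9% answers a different question. An added clause calling the powers unconditional would be an editorial choice. It would leave the boundaries, type I error, event targets and sample size as they are.
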